#### Considerations for making a change

The prevailing consideration for making a change is ensuring the safety of study participants. Additional important considerations for making a change are compliance with GCP, enabling participants to continue safely in the study and maintaining the integrity of the study.

#### **Informed consent**

Additional consent from the participant will be obtained, if required, for

- participation in remote visits, as defined in Section "Remote Visits"
- dispensation of additional study intervention during an extended treatment period
- alternate delivery of study intervention and ancillary supplies, and
- provision of their personal or medical information required prior to implementation of these activities.

#### Changes in study conduct during exceptional circumstances

Changes in study conduct not described in this appendix, or not consistent with applicable local regulations, are not allowed.

The following changes in study conduct will not be considered protocol deviations:

#### Remote visits

Types of remote visits

Telemedicine: Telephone or technology-assisted virtual visits, or both, are acceptable to complete appropriate assessments according to the SoA, if written approval is provided by the sponsor.

Mobile healthcare: Healthcare visits may be performed by a mobile healthcare provider at locations other than the study site when participants cannot travel to the site due to an exceptional circumstance if written approval is provided by the sponsor.

Other alternative locations: Laboratory draws may be done at an alternate location in exceptional circumstances, if written approval is provided by the sponsor.

## Data capture

In source documents and the CRF, the study site should capture the visit method, with a specific explanation for any data missing because of missed in-person site visits.

Safety reporting

Regardless of the type of remote visits implemented, the protocol requirements regarding the reporting of AEs, SAEs, and PCs remain unchanged.

Return to on-site visits

Every effort should be made to enable participants to return to on-site visits as soon as reasonably possible, while ensuring the safety of both the participants and the site staff.

## Local laboratory testing option

Local laboratory testing may be conducted in lieu of central laboratory testing, except for HbA1c and serum glucose testing. Lilly-designated laboratory testing must be retained for HbA1c and serum glucose.

The local laboratory must be qualified in accordance with applicable local regulations.

Obtain local labs for safety hematology, chemistry, hormone panel, and urinalysis, when applicable, per the SoA. Safety labs should be obtained as specified in the SoA.

All labs will be reviewed by the investigators. Sign and date review of local labs per normal process and follow-up with the participant as needed. Results will not be recorded in the CRF.

Lilly Medical should be informed of any labs that meet criteria for temporary or permanent study intervention discontinuation.

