# 10.1.7. Data Quality Assurance

# **Investigator responsibilities**

All participant data relating to the study will be recorded on printed or electronic CRFs unless transmitted to the sponsor or designee electronically, for example, laboratory data.

The investigator is responsible for verifying that data entries are accurate and correct by physically or electronically signing the CRF.

The investigator must maintain accurate documentation (source data) that supports the information entered in the CRF.

The investigator must permit study-related monitoring, audits, IRB/IEC review, and regulatory agency inspections and provide direct access to source data documents.

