# 10.2. Appendix 2: Clinical Laboratory Tests

The clinical laboratory tests will be performed by the Lilly-designated laboratory or by the local laboratory as specified in the table below.

Local laboratory results are only required in the event that the central laboratory results are not available in time for either study intervention administration and/or response evaluation. If a local sample is required, it is important that the sample for central analysis is obtained at the same time. Additionally, if the local laboratory results are used to make either a study intervention decision or response evaluation, the results must be recorded.

In circumstances where the sponsor approves local laboratory testing in lieu of central laboratory testing (in the table below), the local laboratory must be qualified in accordance with applicable local regulations.

Protocol-specific requirements for inclusion or exclusion of participants are detailed in Section 5 of the protocol.

Additional tests may be performed at any time during the study as determined necessary by the investigator or required by local regulations.

Investigators must document their review of the laboratory safety results.

Clinical Laboratory Tests	Comments
Hematology	Assayed by Lilly-designated laboratory
Hemoglobin	
Hematocrit	
Erythrocyte count (RBCs - red blood cells)	
Mean cell volume	
Mean cell hemoglobin	
Mean cell hemoglobin concentration	
Leukocytes (WBCs - white blood cells)	
Differential	
Percent and absolute count of:	
Neutrophils, segmented	
Lymphocytes	
Monocytes	
Eosinophils	
Basophils	
Platelets	
Clinical Chemistry	Assayed by Lilly-designated laboratory
Sodium	
Potassium	
Chloride	
Bicarbonate	
Total bilirubin	
Direct bilirubin	
Alkaline phosphatase (ALP)	
Alanine aminotransferase (ALT)	
Aspartate aminotransferase (AST)	
Gamma-glutamyl transferase (GGT)	
Blood urea nitrogen (BUN)	
Creatinine	
Uric acid	
Total protein	
Albumin	
Calcium	
Phosphorus	
Glucose	Fasting or random (Refer to SoA)
Cholesterol	
Triglycerides	
Lipid Panel	Assayed by Lilly-designated laboratory
High-density lipoprotein (HDL)	
Low-density lipoprotein (LDL-C)	This value will be calculated. If triglycerides >400 mg/dL, the direct LDL will be assayed

Very-low-density lipoprotein (VLDL-C)	
Urinalysis	Assayed by Lilly-designated laboratory
Specific gravity	
рН	
Protein	
Glucose	
Ketones	
Bilirubin	
Urobilinogen	
Blood	
Nitrite	
Urine leukocyte esterase	
Microscopic examination of sediment	
Hormones (female)	

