#### 4.6.3.2. Laboratory and Adverse Event for Hepatic Safety

Hepatic labs include

- alanine aminotransferase (ALT)
- aspartate aminotransferase (AST)
- total bilirubin (TBL)
- direct bilirubin (DBL)
- serum alkaline phosphatase (ALP), and
- gamma-glutamyltransferase (GGT).

When criteria are met for hepatic evaluations, investigators will conduct close monitoring of hepatic symptoms and liver tests, perform a comprehensive evaluation for alternative causes of abnormal liver tests, and complete follow-up hepatic safety CRFs.

The table below lists summary TFLs for the analysis of hepatic laboratory data.

Analysis	Details		
Abnormal postbaseline categories – hepatic safety parameters	ALT: The number and percentage of participants with a measurement greater than or equal to 1 time (1X), 3 times (3X), 5 times (5X), 10 times (10X), and 20 times (20X) the performing laboratory ULN during the postbaseline period will be summarized for all participants with a postbaseline value.		
	AST: The number and percentage of participants with a measurement greater than or equal to 1 time (1X), 3 times (3X), 5 times (5X), 10 times (10X), and 20 times (20X) the performing laboratory ULN during the postbaseline period will be summarized for all participants with a postbaseline value.		
	ALP: The number and percentage of participants with a measurement greater than or equal to 2 times (2X) and 3 times (3X) the performing laboratory ULN during the postbaseline period will be summarized for all participants with a postbaseline value.		
	TBL: The number and percentage of participants with a measurement greater than or equal to 2 times (2X), 5 times (5X), and 8 times (8X) the performing laboratory ULN during the postbaseline period will be summarized for all participants with a postbaseline value.		
	DBL: The number and percentage of participants with a measurement greater than or equal to 2 times (2X) and 5 times (5X) the performing laboratory ULN during the postbaseline period will be summarized for all participants with a postbaseline value.		
	GGT: The number and percentage of participants with a measurement greater than or equal to 2 times (2X) the performing laboratory ULN during the postbaseline period will be summarized for all participants with a postbaseline value.		

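### Protocol Appendix 7 bars CRF entry of local safety laboratory results without exception, while Section 10.2 requires recording of local results that drive a study intervention decision; local-only values have no stated route to the safety tables

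*Protocol*

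**What the plan says.** Protocol Section 10.7 (Appendix 7), under the local laboratory testing option, opens with "Local laboratory testing may be conducted in lieu of central laboratory testing, except for HbA1c and serum glucose testing". It covers safety hematology, chemistry, hormone panel and urinalysis. The investigator reviews and signs the local report, and then: "Results will not be recorded in the CRF". A separate paragraph adds: "Lilly Medical should be informed of any labs that meet criteria for temporary or permanent study intervention discontinuation".

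Protocol Section 10.2 (Appendix 2) has a different rule: "if the local laboratory results are used to make either a study intervention decision or response evaluation, the results must be recorded". It also asks for a parallel central sample ("If a local sample is required, it is important that the sample for central analysis is obtained at the same time"), but it separately provides for substitution ("In circumstances where the sponsor approves local laboratory testing in lieu of central laboratory testing"), subject to the local laboratory being qualified.

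Protocol Section 10.1.7 describes how data reach the sponsor: "All participant data relating to the study will be recorded on printed or electronic CRFs unless transmitted to the sponsor or designee electronically", with laboratory data as its example of electronic transmission.

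SAP Section 4.6.3.2 counts participants at or above multiples of a limit of normal: "the performing laboratory ULN during the postbaseline period will be summarized for all participants with a postbaseline value". SAP Section 4.6.3.3 and SAP Appendix 10 tabulate renal, electrolyte, lipid and hematology abnormalities. Both SAP sections take unscheduled as well as scheduled measurements. Neither says what happens to a local result that is not in the database.

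**The concern.** The test is done, read and signed by the investigator, and may prompt an interruption of study drug, yet its value is kept out of the CRF by a rule. Appendix 7 itself expects some of these results to meet interruption or discontinuation criteria, and the liver criteria in Protocol Section 7.1.1 are numeric. Those are the results that Section 10.2 says must be recorded.

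At stake is the completeness of the laboratory safety tables. A participant with one abnormal local panel and otherwise normal central panels stays in the denominator and counts as normal. A participant whose only postbaseline panel was local leaves the denominator.

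**Working it through.** **1. The recording rules side by side.**

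| Point | Appendix 7 | Section 10.2 |
|---|---|---|
| Local replaces central | Allowed in exceptional circumstances | Foreseen, with sponsor approval |
| Recording | No CRF entry, no exception | Required if used for an intervention decision or response evaluation |
| Place of recording | CRF excluded, no alternative named | Not named |

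Substitution is therefore not in conflict; recording is, and only for decision-driving results. A site could try to satisfy both by recording in source documents alone. Section 10.1.7 points the other way: participant data go on the CRF unless they arrive electronically, and no electronic route is named for local results. Even on the source-only reading, the value does not reach the analysis.

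**2. What other routes would catch.** Protocol Section 8.2.4 requires clinically relevant laboratory changes to be reported as adverse events. Protocol Section 8.2.5 sends some cases to the hepatic safety CRF. Its triggers compare with the SAP 4.6.3.2 tables as follows:

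| Test | Hepatic safety CRF laboratory trigger | SAP table counts |
|---|---|---|
| ALT | ≥5x ULN, or ≥3x baseline if baseline ≥1.5x ULN, on at least 2 consecutive tests | Any value ≥1x, 3x, 5x, 10x, 20x ULN |
| AST | None | Any value ≥1x, 3x, 5x, 10x, 20x ULN |
| ALP | ≥2x ULN (or 2x an elevated baseline) on at least 2 consecutive tests | Any value ≥2x, 3x ULN |
| TBL | Single value ≥2x ULN (or 2x an elevated baseline) | Any value ≥2x, 5x, 8x ULN |
| Direct bilirubin | None | Any value ≥2x, 5x ULN |
| GGT | None | Any value ≥2x ULN |

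The form is also triggered by a serious hepatic event and by discontinuation of study drug for a hepatic event. Temporary interruption is not listed. There is no equivalent form for renal, electrolyte or hematology values.

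**3. Size per participant.** The Schedule of Activities places postbaseline chemistry and hematology at Visits 16, 25, 33 and 802 (Weeks 12, 26, 52 and 57), plus early discontinuation. For a completer that is 4 planned draws, so one local-only panel is 1/4 = 25%. If it were the Week 26 panel, the planned central chemistry would have a gap of 52 − 12 = 40 weeks; this is the longest gap that losing one of the four can leave.

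**4. Size across the trial.** The documents do not say how often the option would be used. Let f be the assumed share of participants who lose one draw. The share of planned draws lost is f × 1/4:

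- f = 5%: 1.25%
- f = 10%: 2.5%
- f = 25%: 6.25%
- f = 50%: 12.5%

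As an illustration, take 670/2 = 335 per arm and assume an abnormality in 1% of participants, visible at only one of the four draws, each equally likely. The expected number on record is 335 × 0.01 × (1 − f/4): 3.35 at f = 0, 3.27 at f = 10% and 2.93 at f = 50%.

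**5. Primary endpoint.** Appendix 7 keeps HbA1c and serum glucose with the central laboratory, so the primary and gated analyses do not depend on this rule.

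**The case against.** The strongest reply is that the gap is narrow and other safeguards exist. Appendix 7 covers rare, temporary situations and needs the sponsor's written approval. Local testing is optional. HbA1c must stay central and is scheduled at all four chemistry visits, so a central sample is still due each time, which makes local-only panels less likely though not impossible. Adverse event reporting is unchanged under Appendix 7. Protocol Section 8.2.5 asks for repeat liver tests within 48 to 72 hours of an abnormal result that meets its criteria, and Protocol Section 10.5 assigns the selected hepatic work-up to the central laboratory, with local testing only in addition. A central repeat would enter the SAP tables as an unplanned measurement. The rule applies to both arms alike. All of this stands, and it limits the size of the problem. It does not remove the conflict, and the documents do not say how Section 10.5 works while Appendix 7 is in force.

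Three stronger readings are tempting and not supported:

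- A reader might infer that every unrecorded local panel breaches Section 10.2. That duty is conditional and does not name the CRF, so a routine panel that drives no decision does not contradict it.
- A reader might infer that study drug could be stopped on a local ALT that leaves no trace. Discontinuation for a hepatic event triggers the hepatic safety CRF whatever the value.
- A reader might infer that the incidence of abnormalities is understated. That follows only if an abnormality appears solely on an unrecorded panel and none of the other routes catches it, and the documents show no mechanism that would distort the difference between arms.

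A last objection concerns pooling. Renal, electrolyte and hematology outputs use absolute cut-offs or change from baseline, and the liver and lipid MMRM works on log values. Mixing assays could create spurious threshold crossings. That is a fair reason not to pool local values there; it is no reason to leave them unrecorded.

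**Conclusion.** The point holds as an inconsistency in recording rules with a limited consequence for the safety data. Appendix 7 bars CRF entry without exception, Section 10.2 requires recording of decision-driving local results, and the passages must be reconciled. Local-only values have no stated route to the database. An abnormality seen only on such a panel would be absent from the SAP threshold tables unless caught by an adverse event report, the hepatic safety CRF or a central repeat. The gap is clearest for AST, GGT and direct bilirubin, for single ALT elevations, and for temporary interruptions.

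The loss is 1 of 4 planned postbaseline draws per affected panel in a completer. The number of participants affected is unknown and may be zero; the trial-level percentages rest on assumed shares. Understated incidence is a possibility, not a finding. The primary and gated analyses are not affected.

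**What to change.** 1. Amend the Appendix 7 sentence so that local results informing a study intervention decision, and all local hepatic results (ALT, AST, ALP, TBL, direct bilirubin, GGT), are entered in the CRF with units, reference range and collection date. This also settles the conflict with Section 10.2.
2. State in SAP 4.6.3.2 that these hepatic values enter its tables, plots and listings. The threshold tables already scale to the performing laboratory's limit of normal, so no new method is needed.
3. Record and list other local values (renal, electrolytes, hematology), and report the number of local-only panels by arm. They need not be pooled into the SAP 4.6.3.3 MMRM or cut-off analyses; the SAP should say so.

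The cost is a protocol wording change, a local-laboratory CRF page, a short SAP addition, and some site data entry at a time when sites may be stretched.

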### Study intervention and ancillary supplies (including participant diaries)

When a participant is unable to go to the site to receive study supplies during normal on-site visits, the site should work with the sponsor to determine appropriate actions. These actions may include

- asking the participant to go to the site and receive study supplies from site staff without completion of a full study visit
- asking the participant's designee to go to the site and receive study supplies on a participant's behalf, and
- arranging delivery of study supplies.

These requirements must be met before action is taken.

- Alternate delivery of study intervention should be performed in a manner that does
  not compromise treatment blinding and ensures product integrity. The existing
  protocol requirements for product accountability remain unchanged, including
  verification of participant's receipt of study supplies.
- When delivering supplies to a location other than the study site, for example, participant's home, the investigator, sponsor, or both, should ensure oversight of the shipping process to ensure accountability and product quality, that is, storage conditions maintained and intact packaging upon receipt.
- Instructions may be provided to the participant or designee on the final disposition of any unused or completed study supplies.

#### Screening period guidance

To ensure safety of study participants, laboratory values and other eligibility assessments taken at screening or the lead-in visits are valid for a maximum of 24 days. The following rules will be applied for active, nonrandomized participants whose participation in the study must be paused due to exceptional circumstances:

- If screening is paused for less than 24 days from the signing of the ICF to the randomization visit, the participant will proceed to the next study visit per the usual SoA, provided that the randomization visit is conducted within 30 days from first screening.
  - The site should conduct the next visit if the participant's eligibility criteria are confirmed, and the site should document the reason for delay.
  - Due to the pause in screening, sites should also reconfirm the impacted participant's consent and document this confirmation in the source documentation.
- If screening is paused for more than 24 days from signing of the ICF to the randomization visit, the participant must be discontinued because of screening interruption due to an exceptional circumstance. This is documented as a screen failure in the CRF. The participant can reconsent and be rescreened as a new participant. The screening procedures per the usual SoA should be followed, starting at the screening visit to ensure participant eligibility by the randomization visit.

#### Adjustments to visit windows

Whenever possible and safe to do so, as determined by the investigator's discretion, participants should complete the usual SoA. To maximize the possibility that these visits can be conducted as on-site visits, the windows for visits may be adjusted, upon further guidance from the sponsor. This minimizes missing data and preserves the intended conduct of the study.

The primary endpoint visit, Week 52 (Visit 33), should be completed per original schedule whenever possible and safe to do so. However, the visit windows should be within  $\pm 7$  days relative to the target visit date.

For participants whose visits have extended windows, additional study intervention may need to be provided to avoid interruption and maintain overall integrity of the study.

#### **Documentation**

Changes to study conduct will be documented

Sites will identify and document the details of how participants, visits types, and conducted activities were affected by exceptional circumstances. Dispensing or shipment records of study intervention and relevant communications, including delegation, should be filed with site study records.

Source documents at alternate locations

Source documents generated at a location other than the study site should be part of the investigator's source documentation and should be transferred to the site in a secure and timely manner.

# 10.8. Appendix 8: Abbreviations and Definitions

Term	Definition
abuse	Use of a study intervention for recreational purposes or to maintain an addiction or dependence
ADA	antidrug antibody
AE	adverse event
ANCOVA	analysis of covariance
authorized IMP	Applicable to the EU only: a medicinal product authorized in accordance with Regulation (EC) No 726/2004 or in any Member State concerned in accordance with Directive 2001/83/EC, irrespective of changes to the labeling of the medicinal product, which is used as an investigational medicinal product
CI	confidence interval
complaint	A complaint is any written, electronic, or oral communication that alleges deficiencies related to the identity, quality, purity, durability, reliability, safety or effectiveness, or performance of a drug or drug delivery system
compliance	Adherence to all study-related, good clinical practice, and applicable regulatory requirements
CRF	case report form; a printed, optical, or electronic document designed to record all of the protocol-required information to be reported to the sponsor for each trial participant
DID-EQ	Diabetes Injection Device Experience Questionnaire
DMC	data monitoring committee; a data-monitoring committee is a group of independent scientists who are appointed to monitor the safety and scientific integrity of a human research intervention and to make recommendations to the sponsor regarding the stopping of a study for efficacy, or for harms, or for futility. The composition of the committee is dependent upon the scientific skills and knowledge required for monitoring the particular study
DPP-4	dipeptidyl peptidase-4
Device deficiencies	equivalent to product complaint
DTSQ-c	Diabetes Treatment Satisfaction Questionnaire - Change Version
DTSQ-s	Diabetes Treatment Satisfaction Questionnaire-Status Version
EAS	efficacy analysis set
ECG	electrocardiogram

**ED** early discontinuation

**EDC** electronic data capture

eGFR (CKD-EPI) estimated glomerular filtration rate (chronic kidney disease epidemiology

collaboration)

**enroll** The act of assigning a participant to a treatment. Participants who are enrolled in the

study are those who have been assigned to a treatment

**enter** Participants entered into a study are those who sign the informed consent form directly

or through their legally acceptable representatives

**ERB** Ethical Review Board

**FBG** fasting blood glucose

GCP good clinical practice

GLP-1 glucagon-like peptide-1

GLP-1 RA GLP-1 receptor agonist

HbA1c hemoglobin A1c

IB Investigator's Brochure

**ICF** informed consent form

ICH International Council for Harmonisation

**IEC** Independent Ethics Committee

IMP investigational medicinal product

A medicinal product, which is being tested or used as a reference, including as a

placebo, in a clinical trial.

See also "investigational product."

**informed consent** A process by which a participant voluntarily confirms their willingness to participate

in a particular study, after having been informed of all aspects of the study that are relevant to the participant's decision to participate. Informed consent is documented by

means of a written, signed, and dated informed consent form

interim analysis An interim analysis is an analysis of clinical study data, separated into treatment

groups, that is conducted before the final reporting database is created or locked

investigational A pharmaceutical form of an active ingredient or placebo being tested or used as a product reference in a clinical trial, including products already on the market when used or

reference in a clinical trial, including products already on the market when used or assembled (formulated or packaged) in a way different from the authorized form, or marketed products used for an unauthorized indication, or marketed products used to

gain further information about the authorized form. See also "IMP".

**IRB** Institutional Review Board

**IWRS** interactive web-response system

LS least squares

medication error Errors in the prescribing, dispensing, or administration of a study intervention,

regardless of whether or not the medication is administered to the participant or the error leads to an AE. Medication error generally involves a failure to uphold 1 or more of the 5 "rights" of medication use: the right participant, the right drug, the right dose,

right route, and at the right time.

In addition to the core 5 rights, the following may also represent medication errors:

• dose omission associated with an AE or a product complaint

• dispensing or use of expired medication

• use of medication past the recommended in-use date

• dispensing or use of an improperly stored medication

• use of an adulterated dosage form or administration technique inconsistent with the medication's labeling (for example, Summary of Product Characteristics, IB, local label, and protocol), or

• shared use of cartridges, prefilled pens, or both.

misuse use of a study intervention for self-treatment that either is inconsistent with the

prescribed dosing regimen, indication, or both, or is obtained without a prescription

MMRM mixed-model repeated measures

**NIM** noninferiority margin

participant equivalent to CDISC term "subject": an individual who participates in a clinical trial,

either as recipient of an investigational medicinal product or as a control

PC product complaint

**PK/PD** pharmacokinetics/pharmacodynamics

**PT-INR** prothrombin time, INR

SAE serious adverse event

**SAP** statistical analysis plan

screen The act of determining if an individual meets minimum requirements to become part

of a pool of potential candidates for participation in a clinical study

SGLT2 sodium-glucose cotransporter 2

SIM-Q Simplicity of Diabetes Treatment Questionnaire

**SMBG** self-monitoring of blood glucose

**T1D** Type 1 diabetes

**T2D** Type 2 diabetes

TE ADA treatment-emergent ADA

**TEAE** treatment-emergent adverse event: an untoward medical occurrence that emerges

during a defined treatment period, having been absent pretreatment, or worsens relative to the pretreatment state, and does not necessarily have to have a causal

relationship with this treatment

**TRIM-D** Treatment-Related Impact Measure – Diabetes

**WOCBP** women of childbearing potential

